**Table 21: Medical History – mITT Subjects**

Medical History SOC and Preferred Term	ASP8062 (N=xx)	Placebo (N=xx)	Total (N=xx)
SOC	xx (xx.x%)	xx (xx.x%)	xx (xx.x%)
Preferred term name	xx (xx.x%)	xx (xx.x%)	xx (xx.x%)

**Table 22: Baseline POMS – mITT Subjects**

Characteristic	ASP8062 (N=xx)	Placebo (N=xx)	Total (N=xx)	p-value
Tension-Anxiety				0.xxx
N	xx	xx	xx	
Mean	xx.x	xx.x	xx.x	
SD 	xxx.xx	xxx.xx	xxx.xx	
Median	xx	xx	xx	
Min-Max	(xx-xx)	(xx-xx)	(xx-xx)	
Scale Min-Max			(xx-xx)	
Depression-Dejection				0.xxx
N	xx	xx	xx	
Mean	xx.x	xx.x	xx.x	
SD	xxx.xx	xxx.xx	xxx.xx	
Median	xx	xx	xx	
Min-Max	(xx-xx)	(xx-xx)	(xx-xx)	
Scale Min-Max			(xx-xx)	
Anger-Hostility				0.xxx
N	xx	xx	xx	
Mean	xx.x	xx.x	xx.x	
SD	xxx.xx	xxx.xx	xxx.xx	
Median	xx	xx	xx	
Min-Max	(xx-xx)	(xx-xx)	(xx-xx)	
Scale Min-Max			(xx-xx)	
Fatigue-Inertia				0.xxx
N	xx	xx	xx	
Mean	xx.x	xx.x	xx.x	
SD	xxx.xx	xxx.xx	xxx.xx	
Median	xx	xx	xx	
Min-Max	(xx-xx)	(xx-xx)	(xx-xx)	
Scale Min-Max			(xx-xx)	
Confusion-Bewilderment				0.xxx
N	xx	xx	xx	
Mean	xx.x	xx.x	xx.x	
SD	xxx.xx	xxx.xx	xxx.xx	

Characteristic	ASP8062 (N=xx)	Placebo (N=xx)	Total (N=xx)	p-value 
Median	xx	xx	xx	
Min-Max	(xx-xx)	(xx-xx)	(xx-xx)	
Scale Min-Max			(xx-xx)	
Vigor-Activity				0.xxx
N	xx	xx	xx	
Mean	xx.x	xx.x	xx.x	
SD	xxx.xx	xxx.xx	xxx.xx	
Median	xx	xx	xx	
Min-Max	(xx-xx)	(xx-xx)	(xx-xx)	
Scale Min-Max			(xx-xx)	
Total Mood Disturbance				0.xxx
N	xx	xx	xx	
Mean	xx.x	xx.x	xx.x	
SD	xxx.xx	xxx.xx	xxx.xx	
Median	xx	xx	xx	
Min-Max	(xx-xx)	(xx-xx)	(xx-xx)	
Scale Min-Max			(xx-xx)	

 t-test

SD is standard deviation

**Table 23: Baseline POMS – Evaluable Subjects**

Same as Table 22

**Table 24: Baseline PSQI – mITT Subjects**

Characteristic	ASP8062	Placebo	Total	p-value 
Overall Sleep Experience				0.xxx
N	xx	xx	xx	
Mean	xx.x	xx.x	xx.x	
SD 	xxx.xx	xxx.xx	xxx.xx	
Median	xx	xx	xx	
Min-Max	(xx-xx)	(xx-xx)	(xx-xx)	

Characteristic	ASP8062	Placebo	Total	p-value 
Scale Min-Max			(xx-xx)	

 t-test

 SD is standard deviation

**Table 25: Baseline PSQI – Evaluable Subjects**

Same as Table 24

**Table 26: Baseline Drinking-related Behavior and Characteristics – mITT Subjects**

	ASP8062	Placebo	Total	
Characteristic	(N=xx)	(N=xx)	(N=xx)	p-value
Drinking Goal (n, %)				
Stop Drinking	xx (xx.x)	xx (xx.x)	xx (xx.x)	
Reduce but not stop	xx (xx.x)	xx (xx.x)	xx (xx.x)	
Goal of no heavy drinking days (n, %)				
Yes	xx (xx.x)	xx (xx.x)	xx (xx.x)	
No	xx (xx.x)	xx (xx.x)	xx (xx.x)	
# Drinks/Week Goal in Subjects that Want to Reduce Drinking				
N	xx	xx	xx	0.xxx
Mean	xx.x	xx.x	xx.x	
SD 	xxx.xx	xxx.xx	xxx.xx	
Median	xx	xx	xx	
Min-Max	(xx-xx)	(xx-xx)	(xx-xx)	
Motivation to achieve goal				
N	xx	xx	xx	0.xxx
Mean	xx.x	xx.x	xx.x	
SD	xxx.xx	xxx.xx	xxx.xx	
Median	xx	xx	xx	
Min-Max	(xx-xx)	(xx-xx)	(xx-xx)	
Confidence in achieving goal				
N	xx	xx	xx	0.xxx
Mean	xx.x	xx.x	xx.x	
SD	xxx.xx	xxx.xx	xxx.xx	
Median	xx	xx	xx	
Min-Max	(xx-xx)	(xx-xx)	(xx-xx)	
AUD Symptom Severity (n, %)				0.xxx
Moderate (4 or 5 symptoms)	xx (xx.x)	xx (xx.x)	xx (xx.x)	
Severe (6 or more symptoms)	xx (xx.x)	xx (xx.x)	xx (xx.x)	
AUD Number of Symptoms (n, %)				
4	xx (xx.x)	xx (xx.x)	xx (xx.x)	
5	xx (xx.x)	xx (xx.x)	xx (xx.x)	
6	xx (xx.x)	xx (xx.x)	xx (xx.x)	
7	xx (xx.x)	xx (xx.x)	xx (xx.x)	
8	xx (xx.x)	xx (xx.x)	xx (xx.x)	
9	xx (xx.x)	xx (xx.x)	xx (xx.x)	
10	xx (xx.x)	xx (xx.x)	xx (xx.x)	

	ASP8062	Placebo	Total	
Characteristic	(N=xx)	(N=xx)	(N=xx)	p-value
11	xx (xx.x)	xx (xx.x)	xx (xx.x)	
AUD Number of Symptoms (continuous)				0.xxx
Mean	xx.x	xx.x	xx.x	
SD	xxx.xx	xxx.xx	xxx.xx	
Median	xx	xx	xx	

Note: Percentages are based on the number of non-missing values in each variable.

 t-test

SD is standard deviation

**Table 27: Baseline Drinking-related Behavior and Characteristics – Evaluable Subjects**

Same as Table 26

**Table 28: Baseline Drinking by TLFB – mITT Subjects**

	ASP8062	Placebo	Total	
Parameter	(N=xx)	(N=xx)	(N=xxx)	p-value
Drinks/Week (Pre-screening Days -1 to -28)				0.xxx
Mean	xx.x	xx.x	xx.x	
SD 	xx.x	xx.x	xx.x	
Median	xx.x	xx.x	xx.x	
Min-Max	(xx-xx)	(xx-xx)	(xx-xx)	
Drinks/Week (7 Days Prior to Randomization)				0.xxx
Mean	xx.x	xx.x	xx.x	

	ASP8062	Placebo	Total	
Parameter	(N=xx)	(N=xx)	(N=xxx)	p-value
SD	xx.x	xx.x	xx.x	
Median	xx.x	xx.x	xx.x	
Min-Max	(xx-xx)	(xx-xx)	(xx-xx)	
Drinks/Week (Percent Change Pre-screening Days -1 to -28 to 7 Days Prior to Randomization)				0.xxx
Mean	xx.x	xx.x	xx.x	
SD	xx.x	xx.x	xx.x	
Median	xx.x	xx.x	xx.x	
Min-Max	(xx-xx)	(xx-xx)	(xx-xx)	
Drinks/Drinking Day (Pre-screening Days -1 to -28)				0.xxx
Mean	xx.x	xx.x	xx.x	
SD	xx.x	xx.x	xx.x	
Median	xx.x	xx.x	xx.x	
Min-Max	(xx-xx)	(xx-xx)	(xx-xx)	
Drinks/Drinking Day (7 Days Prior to Randomization)				0.xxx
Mean	xx.x	xx.x	xx.x	
SD	xx.x	xx.x	xx.x	
Median	xx.x	xx.x	xx.x	
Min-Max	(xx-xx)	(xx-xx)	(xx-xx)	
Drinks/Drinking Day (Percent Change Pre-screening Days -1 to -28 to 7 Days Prior to Randomization)				0.xxx
Mean	xx.x	xx.x	xx.x	
SD	xx.x	xx.x	xx.x	
Median	xx.x	xx.x	xx.x	
Min-Max	(xx-xx)	(xx-xx)	(xx-xx)	
Percentage of Heavy Drinking Days (Pre-screening Days -1 to -28)				0.xxx
Mean	xx.x%	xx.x%	xx.x%	
SD	xx.x%	xx.x%	xx.x%	
Median	xx.x%	xx.x%	xx.x%	
Min-Max	(xx%-xx%)	(xx%-xx%)	(xx%-xx%)	
Percentage of Very Heavy Drinking Days (Pre-screening Days -1 to -28)				0.xxx
Mean	xx.x%	xx.x%	xx.x%	

	ASP8062	Placebo	Total	
Parameter	(N=xx)	(N=xx)	(N=xxx)	p-value
SD	xx.x%	xx.x%	xx.x%	
Median	xx.x%	xx.x%	xx.x%	
Min-Max	(xx%-xx%)	(xx%-xx%)	(xx%-xx%)	
Percentage Days Abstinent (Pre-screening Days -1 to -28)				0.xxx
Mean	xx.x%	xx.x%	xx.x%	
SD	xx.x%	xx.x%	xx.x%	
Median	xx.x%	xx.x%	xx.x%	
Min-Max	(xx%-xx%)	(xx%-xx%)	(xx%-xx%)	
WHO Risk Level				0.xxx
High Risk	xx (xx.x%)	xx (xx.x%)	xx (xx.x%)	
Very High Risk	xx (xx.x%)	xx (xx.x%)	xx (xx.x%)	

Note: Percentages are based on the number of non-missing values in each variable.

Chi-square test for categorical variables and t-test for continuous variables

 SD is standard deviation

**Table 29: Baseline Drinking by TLFB – Evaluable Subjects**

Same as Table 28

**Table 30: Baseline Alcohol-Related Craving, Consequences, Withdrawal and Hyperkatifeia – mITT Subjects**

	ASP8062	Placebo	Total	
Parameter	(N=xx)	(N=xx)	(N=xxx)	p-value
Pre-cue ACQ-SF-R^2				0.xxx
Mean	xx.x	xx.x	xx.x	
SD 	xx.x	xx.x	xx.x	
Median	xx.x	xx.x	xx.x	
Min-Max	(xx-xx)	(xx-xx)	(xx-xx)	
Scale Min-Max			(xx.x – xx.x)	
Post-cue ACQ-SF-R				0.xxx
Mean	xx.x	xx.x	xx.x	
SD	xx.x	xx.x	xx.x	
Median	xx.x	xx.x	xx.x	
Min-Max	(xx-xx)	(xx-xx)	(xx-xx)	
Pre-Post ACQ-SF-R				
Mean	xx.x	xx.x	xx.x	
SD	xx.x	xx.x	xx.x	
Median	xx.x	xx.x	xx.x	
Min-Max	(xx-xx)	(xx-xx)	(xx-xx)	
PROMIS Alcohol Negative Consequences (T-scores)				0.xxx
Mean	xx.x	xx.x	xx.x	
SD	xx.x	xx.x	xx.x	
Median	xx.x	xx.x	xx.x	
Min-Max	(xx-xx)	(xx-xx)	(xx-xx)	
PACS				0.xxx
Mean	xx.x	xx.x	xx.x	
SD	xx.x	xx.x	xx.x	
Median	xx.x	xx.x	xx.x	
Min-Max	(xx-xx)	(xx-xx)	(xx-xx)	
Scale Min-Max			(xx.x – xx.x)	
CIWA-AR^6				0.xxx
Mean	xx.x	xx.x	xx.x	
SD	xx.x	xx.x	xx.x	
Median	xx.x	xx.x	xx.x	
Min-Max	(xx-xx)	(xx-xx)	(xx-xx)	
Scale Min-Max			(xx.x – xx.x)	

	ASP8062	Placebo	Total	
Parameter	(N=xx)	(N=xx)	(N=xxx)	p-value
Withdrawal Symptoms (CIWA <math>\geq</math> 10)	xx (xx.x%)	xx (xx.x%)	xx (xx.x%)	0.xxx
Hyperkatifeia				0.xxx
Mean	xx.x	xx.x	xx.x	
SD	xx.x	xx.x	xx.x	
Median	xx.x	xx.x	xx.x	
Min-Max	(xx-xx)	(xx-xx)	(xx-xx)	
Scale Min-Max			(xx.x – xx.x)	
Stress Anxiety				0.xxx
Mean	xx.x	xx.x	xx.x	
SD	xx.x	xx.x	xx.x	
Median	xx.x	xx.x	xx.x	
Min-Max	(xx-xx)	(xx-xx)	(xx-xx)	
Scale Min-Max			(xx.x – xx.x)	
Depression				0.xxx
Mean	xx.x	xx.x	xx.x	
SD	xx.x	xx.x	xx.x	
Median	xx.x	xx.x	xx.x	
Min-Max	(xx-xx)	(xx-xx)	(xx-xx)	
Scale Min-Max			(xx.x – xx.x)	
Irritable				0.xxx
Mean	xx.x	xx.x	xx.x	
SD	xx.x	xx.x	xx.x	
Median	xx.x	xx.x	xx.x	
Min-Max	(xx-xx)	(xx-xx)	(xx-xx)	
Scale Min-Max			(xx.x – xx.x)	
Pain				0.xxx
Mean	xx.x	xx.x	xx.x	
SD	xx.x	xx.x	xx.x	
Median	xx.x	xx.x	xx.x	
Min-Max	(xx-xx)	(xx-xx)	(xx-xx)	
Scale Min-Max			(xx.x – xx.x)	

 t-test for continuous variables and chi-square test for categorical

ACQ-SF-R is Alcohol Craving Questionnaire – Short Form – Revised

 SD is standard deviation

 PROMIS is short form of Patient-reported Outcomes Information System

 PACS is Penn Alcohol Craving Scale  CIWA-AR is Clinical Institute Withdrawal Assessment for Alcohol-revised

**Table 31: Baseline Alcohol-Related Craving, Consequences, Withdrawal and Hyperkatifeia – Evaluable Subjects**

Same as Table 30

**Table 32: Baseline Other Substance Use – mITT Subjects**

	ASP8062	Placebo	Total	p-value 
Parameter	(N=xx)	(N=xx)	(N=xxx)	
Smoker (n, %)	xx (xx)	xx (xx)	xx (xx)	0.xxx
Days Smoked in the Past Week				
Mean	XX.X	XX.X	XX.X	
SD 	XX.X	XX.X	XX.X	
Median	XX.X	XX.X	XX.X	
(Min-Max)	(xx-xx)	(xx-xx)	(xx-xx)	
Average Cigarettes Smoked Per Week (among Smokers)				0.xxx
Mean	XX.X	XX.X	XX.X	
SD	XX.X	XX.X	XX.X	
Median	XX.X	XX.X	XX.X	
Min-Max	(xx-xx)	(xx-xx)	(xx-xx)	
Any Other Nicotine Product Use (doesn't include cigarettes) (n, %)	xx (xx)	xx (xx)	xx (xx)	0.xxx
Days Used Other Nicotine Products Per Week				0.xxx
Mean	XX.X	XX.X	XX.X	
SD	XX.X	XX.X	XX.X	
Median	XX.X	XX.X	XX.X	
Min-Max	(xx-xx)	(xx-xx)	(xx-xx)	
Any Nicotine Use (cigarettes + other) (n, %)	xx (xx)	xx (xx)	xx (xx)	0.xxx
THC				0.xxx
Negative	xx (xx.x%)	xx (xx.x%)	xx (xx.x%)	
Positive	xx (xx.x%)	xx (xx.x%)	xx (xx.x%)	

Note: Percentages are based on the number of non-missing values in each variable.

t-test for continuous variables and chi-square test for categorical

 SD is standard Deviation

**Table 33: Baseline Other Substance Use – Evaluable Subjects**

Same as Table 32

### **12.1.3. Primary Efficacy Endpoint**

**Table 34: Week 3 Strength of Craving Scores – mITT Subjects**

		ASP8062 N=xx	Placebo N=xx	Total N=xx
Cue	Statistic			
Water				
	Mean (SD  )	xx.x (xx.xx)	xx.x (xx.xx)	xx.x (xx.xx)
	Median	xx	xx	xx
	Min-Max	(xx-xx)	(xx-xx)	(xx-xx)
Alcohol				
	Mean (SD)	xx.x (xx.xx)	xx.x (xx.xx)	xx.x (xx.xx)
	Median	xx	xx	xx
	Min-Max	(xx-xx)	(xx-xx)	(xx-xx)
Alcohol - Water				
	Mean (SD)	xx.x (xx.xx)	xx.x (xx.xx)	xx.x (xx.xx)
	Median	xx	xx	xx
	Min-Max	(xx-xx)	(xx-xx)	(xx-xx)

 SD is standard deviation

**Table 35: Week 3 Strength of Craving Scores – Evaluable Subjects**

Same as Table 34

**Table 36: ANCOVA Strength of Craving – mITT Subjects****Type III Wald Tests**

Parameter	Num DF 	Den DF 	F Value	p-value
Arm	1	xx	xxx.xx	0.xxx
Site	xx	xx	xxx.xx	0.xxx
Baseline Cue 	1	xx	xxx.xx	0.xxx

Numerator degrees of freedom;  Denominator degrees of freedom^3 Baseline Cue is the baseline equivalent of the outcome obtained after the presentation of the first alcohol cue at baseline**Least Squares Means**

Arm	Estimate	SE 	95% CI		Difference	SE	p-value 	Cohen's d
			Lower CI	Upper CI				
ASP8062	xx.xx	0.xxx	0.xxx	0.xxx	x.XXX	x.XXX	0.xxx	xx.XXX
Placebo	xx.xx	0.xxx	0.xxx	0.xxx				

 SE is standard error;  Wald test;

**Table 37: ANCOVA Strength of Craving – Evaluable Subjects**

Follow the same analysis as Table 36

#### **12.1.4. Confirmatory Secondary Efficacy Endpoints**

**Table 38: ANCOVA Strength of Craving (Difference Alcohol-Water) – mITT Subjects****Type III Wald Test**

Parameter	Num DF 	Den DF 	F Value	p-value
Arm	1	xx	xxx.xx	0.xxx
Site	xx	xx	xxx.xx	0.xxx
Baseline Cue	1	xx	xxx.xx	0.xxx

Numerator degrees of freedom;  Denominator degrees of freedom

 Baseline Cue is the baseline equivalent of the outcome obtained after the presentation of the first alcohol cue at baseline

**Least Squares Means**

Arm	Estimate	SE 	95% CI		Difference	SE	p-value 	Cohen's d
			Lower CI	Upper CI				
ASP8062	xx.xx	0.xxx	0.xxx	0.xxx	x.xxx	x.xxx	0.xxx	xx.xxx
Placebo	xx.xx	0.xxx	0.xxx	0.xxx				

 SE is standard error;  Wald test;

**Table 39: ANCOVA Strength of Craving (Difference Alcohol-Water) – Evaluable Subjects**

Same as Table 38

**Table 40: Drinking Makes Things Perfect Scores – mITT Subjects**

		ASP8062 N=xx	Placebo N=xx	Total N=xx
Cue	Statistic			
Water				
	Mean (SD  )	xx.x (xx.xx)	xx.x (xx.xx)	xx.x (xx.xx)
	Median	xx	xx	xx
	Min-Max	(xx-xx)	(xx-xx)	(xx-xx)
Alcohol				
	Mean (SD)	xx.x (xx.xx)	xx.x (xx.xx)	xx.x (xx.xx)
	Median	xx	xx	xx
	Min-Max	(xx-xx)	(xx-xx)	(xx-xx)
Alcohol- Water				
	Mean (SD)	xx.x (xx.xx)	xx.x (xx.xx)	xx.x (xx.xx)
	Median	xx	xx	xx
	Min-Max	(xx-xx)	(xx-xx)	(xx-xx)

 SD is standard deviation

**Table 41: Drinking Makes Things Perfect Scores – Evaluable Subjects**

Same as Table 40

**Table 42: ANCOVA Drinking Makes Things Perfect – mITT Subjects****Type III Wald Test**

Parameter	Num DF 	Den DF 	F Value	p-value
Arm	1	xx	xxx.xx	0.xxx
Site	2	xx	xxx.xx	0.xxx
Baseline Cue	1	xx	xxx.xx	0.xxx

Numerator degrees of freedom;  Denominator degrees of freedom^3 Baseline Cue is the baseline equivalent of the outcome obtained after the presentation of the first alcohol cue at baseline**Least Squares Means**

Arm	Estimate	SE 	95% CI		Difference	SE	p-value 	Cohen's d
			Lower CI	Upper CI				
ASP8062	xx.xx	0.xxx	0.xxx	0.xxx	x.xxx	x.xxx	0.xxx	xx.xxx
Placebo	xx.xx	0.xxx	0.xxx	0.xxx				

 SE is standard error;  Wald test;

**Table 43: ANCOVA Drinking Makes Things Perfect – Evaluable Subjects**

Same analysis as Table 42

**Table 44: ANCOVA Drinking Makes Things Perfect (Difference Alcohol-Water) – mITT Subjects****Type III Wald Test**

Parameter	Num DF 	Den DF 	F Value	p-value
Arm	2	xx	xxx.xx	0.xxx
Site	2	xx	xxx.xx	0.xxx
Baseline Cue	1	xx	xxx.xx	0.xxx

Numerator degrees of freedom;  Denominator degrees of freedom

 Baseline Cue is the baseline equivalent of the outcome obtained after the presentation of the first alcohol cue at baseline

**Least Squares Means**

Arm	Estimate	SE 	95% CI		Difference	SE	p-value 	Cohen's d
			Lower CI	Upper CI				
ASP8062	xx.xx	0.xxx	0.xxx	0.xxx	x.xxx	x.xxx	0.xxx	xx.xxx
Placebo	xx.xx	0.xxx	0.xxx	0.xxx				

 SE is standard error;  Wald test;

**Table 45: ANCOVA Drinking Makes Things Perfect (Difference Alcohol-Water) – Evaluable Subjects**

Same analysis as Table 44

**Table 46: Drink Now Scores– mITT Subjects**

		ASP8062 N=xx	Placebo N=xx	Total N=xx
Cue	Statistic			
Water				
	Mean (SD  )	xx.x (xx.xx)	xx.x (xx.xx)	xx.x (xx.xx)
	Median	xx	xx	xx
	Min-Max	(xx-xx)	(xx-xx)	(xx-xx)
Alcohol				
	Mean (SD)	xx.x (xx.xx)	xx.x (xx.xx)	xx.x (xx.xx)
	Median	xx	xx	xx
	Min-Max	(xx-xx)	(xx-xx)	(xx-xx)
Alcohol - Water				
	Mean (SD)	xx.x (xx.xx)	xx.x (xx.xx)	xx.x (xx.xx)

		ASP8062 N=xx	Placebo N=xx	Total N=xx
	Median	xx	xx	xx
	Min-Max	(xx-xx)	(xx-xx)	(xx-xx)

 SD is standard deviation

**Table 47: Drink Now Scores – Evaluable Subjects**

Same as Table 46

**Table 48: ANCOVA Drink Now – mITT Subjects**

**Type III Wald Test**

Parameter	Num DF 	Den DF 	F Value	p-value
Arm	1	xx	xxx.xx	0.xxx
Site	xx	xx	xxx.xx	0.xxx
Baseline Cue	1	xx	xxx.xx	0.xxx

Numerator degrees of freedom;  Denominator degrees of freedom

 Baseline Cue is the baseline equivalent of the outcome obtained after the presentation of the first alcohol cue at baseline

### Least Squares Means

Arm	Estimate	SE 	95% CI		Difference	SE	p-value 	Cohen's d
			Lower CI	Upper CI				
ASP8062	xx.xx	0.xxx	0.xxx	0.xxx	x.xxx	x.xxx	0.xxx	xx.xxx
Placebo	xx.xx	0.xxx	0.xxx	0.xxx				

 SE is standard error;  Wald test;

**Table 49: ANCOVA Drink Now – Evaluable Subjects**

Same analysis as Table 48

**Table 50: ANCOVA Drink Now (Difference Alcohol-Water) – mITT Subjects**

Same analysis as Table 44 with difference as the dependent variable

**Table 51: ANCOVA Drink Now (Difference Alcohol-Water) – Evaluable Subjects**

Same analysis as Table 50

**Table 52: Turn Down Drink Scores – mITT Subjects**

Same analysis as Table 46

**Table 53: Turn Down Drink Scores – Evaluable Subjects**

Same analysis as Table 52

**Table 54: ANCOVA Turn Down Drink – mITT Subjects**

Same analysis as Table 48

**Table 55: ANCOVA Turn Down Drink – Evaluable Subjects**

Same analysis as Table 54

**Table 56: ANCOVA Turn Down Drink (Difference Alcohol-Water) – mITT Subjects**

Same analysis as Table 44

**Table 57: ANCOVA Turn Down Drink (Difference Alcohol-Water) – Evaluable Subjects**

Same analysis as Table 56

**Table 58: Average of Cue Scores – mITT Subjects**

Same analysis as Table 46

**Table 59: Average of Cue Scores – Evaluable Subjects**

Same as Table 58

**Table 60: ANCOVA Average of Cue Scores – mITT Subjects**

Same analysis as Table 48

**Table 61: ANCOVA Average of Cue Scores – Evaluable Subjects**

Same analysis as Table 60

**Table 62: ANCOVA Average of Cue Scores (Difference Alcohol-Water) – mITT Subjects**

Same analysis as Table 44

**Table 63: ANCOVA Average of Cue Scores (Difference Alcohol-Water) – Evaluable Subjects**

Same analysis as Table 62

**Table 64: Beverage Liking Scores – mITT Subjects**

Same analysis as Table 46

**Table 65: Beverage Liking Scores – Evaluable Subjects**

Same analysis as Table 64

### **12.1.5. Secondary Efficacy Endpoints**

**Table 66: Percentage of Subjects No Heavy Drinking Days Weeks 3-6 – mITT Subjects**

	ASP8062	Placebo	Total
	(N=xx)	(N=xx)	(N=xxx)
No Heavy Drinking Days			
Yes	xx (xx.x%)	xx (xx.x%)	xx (xx.x%)
No	xx (xx.x%)	xx (xx.x%)	xx (xx.x%)

**Table 67: Percentage of Subjects with No Heavy Drinking Days Weeks 3-6 – Full Model Logistic Regression (mITT)**

									95% CI	
Parameter		DF	Estimate	Standard Error	Wald Chi-Square	Pr > Chi-Square	Cohen's h	OR^2	Upper	Lower
Intercept		1	xx.xxx	xx.xxx	xx.xxx	0.xxx				
Treatment	Overall	X	xx.xxx	xx.xxx	xx.xxx	0.xxx				
Treatment 	ASP8062	X	xx.xxx	xx.xxx	xx.xxx	0.xxx	0.xxx	xx.xxx	xx.xxx	xx.xxx
Site	Overall	X	xx.xxx	xx.xxx	xx.xxx	0.xxx				
Site 	1	X	xx.xxx	xx.xxx	xx.xxx	0.xxx		xx.xxx	xx.xxx	xx.xxx
Site	2	X	xx.xxx	xx.xxx	xx.xxx	0.xxx		xx.xxx	xx.xxx	xx.xxx

									95% CI 	
Parameter		DF 	Estimate	Standard Error	Wald Chi-Square	Pr > Chi-Square	Cohen's h	OR 	Upper	Lower
Cov		X	xx.XXX	xx.XXX	xx.XXX	0.XXX		xx.XXX	xx.XXX	xx.XXX

 DF is degrees of freedom;  OR is odds ratio;  CI is confidence interval;  Comparison to placebo;

 Site 3 is reference for the OR

*Programming note: COV is baseline equivalent of dependent variable and any other covariate(s) which have not been specified at the time of writing of SAP*

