Continuous secondary endpoints (percent heavy drinking days, percent very heavy drinking days, percent days abstinent, drinks per week, drinks per drinking day, number of cigarettes smoked per week, PACS, POMS, and PSQI score) during the last 4 weeks of treatment period will be analyzed using a mixed-effects model with site, assessment time, and baseline drinking as fixed factors. PROMIS will be analyzed with analysis of covariance model with baseline and treatment as factors. Models will also include time by treatment group interaction term. Additional covariates may be included that are significantly correlated with outcome and/or if there are differences across the treatment groups.

Analysis of the dichotomous secondary endpoints (percentage subjects with no heavy drinking days, percentage subjects abstinent from alcohol, percentage of subjects achieving at least a one and two-level shift in WHO alcohol consumption, and percentage of subjects with no nicotine use among subjects with any use during the week before randomization) during the last 4 weeks of treatment period will be conducted via logistic regression. Covariates may be included provided there are a sufficient number of events.

No imputation for missing endpoint data will be performed for secondary endpoints.

Safety Analyses: AEs will be coded using the most recent version of the Medical Dictionary of Regulatory Activities (MedDRA) preferred terms and will be grouped by system, organ, and class (SOC) designation. The severity, frequency, and relationship of AEs to investigational product will be presented by preferred term by SOC grouping. Listings of each individual AE including start date, stop date, severity, relationship, outcome, and duration will be provided. Each AE (based on preferred terminology) will be counted once only for a given

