#### **9.4.3.1. Secondary Drinking Endpoints**

Percentage of days abstinent per week, percentage of subjects abstinent, percentage of heavy drinking days per week, percentage of very heavy drinking days, weekly mean number of drinks per week, and weekly mean number of drinks per drinking day will be analyzed using the mixed effects model specified in Section 9.4.3. Covariates for these models will be identified as in Section 9.4.4.

Percentage of subjects with a WHO 1-level decrease, and WHO 2-level decrease in alcohol consumption risk category will be analyzed during the last 4 weeks of the maintenance period (Weeks 2 through 5) using a logistic regression model. Covariates for the logistic regression will be identified as in Section 9.4.4. 2x2 contingency tables will report the WHO 1-level decrease, and WHO 2-level decrease along with Cohen's h, odds ratios and 95% CIs. The Wald statistic will be used to test for treatment differences.

No adjustment for multiple comparisons and no imputation will be used for these endpoints.

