#### **9.4.3.3. Smoking and Any Nicotine Use**

The mean number of cigarettes smoked in the past week is measured weekly. The sample is the mITT subjects who smoked at baseline. The data will be analyzed as described in Section 9.4.3. Covariates for this endpoint will be identified in Section 9.4.4. Amount of other nicotine products is not captured, only number of days of use of other nicotine products. The analysis of days of use in subjects using other nicotine products at baseline will use the same method as cigarettes smoked. In addition, 2 tables will examine the number of subjects that are abstinent from cigarettes and any nicotine product use. There will be one logistic regression, if there are sufficient number of subjects abstaining from nicotine use, with abstaining as the dependent variable and covariates as described in Section 9.4.4. No imputation will be used for these endpoints.

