**Table 69: Percentage of Subjects Abstinent from Alcohol Weeks 3-6 – Full Model Logistic Regression (mITT)**

Presented in same manner as Table 67 *programming note: baseline PDA is a covariate for PSA outcome*

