**Table 85: Mean Cigarettes Smoked Among Smokers (mITT) – Full Model, Mixed Effects, Weeks 3-6**

**Table 86: PACS (mITT) – Weeks 3-6**

**Table 87: PACS (mITT) – Full Model, Mixed Effects, Weeks 3-6**

**Table 88: Percentage of Subjects Abstinent from Nicotine Use Weeks 3-6 – Among Subjects that Used Nicotine Products at Baseline**

	ASP8062	Placebo	Total
	(N=xx)	(N=xx)	(N=xxx)
No Nicotine Use			
Yes	xx (xx.x%)	xx (xx.x%)	xx (xx.x%)
No	xx (xx.x%)	xx (xx.x%)	xx (xx.x%)

 Nicotine use includes cigarettes or other nicotine products

**Table 89: Percentage of Subjects Abstinent from Nicotine Use Weeks 3-6 – Full Model Logistic Regression (Among Nicotine Users at Baseline)**

									95% CI 	
Parameter		DF 	Estimate	Standard Error	Wald Chi-Square	Pr > Chi-Square	Cohen's h	OR 	Upper CI	Lower CI
Intercept		1	xx.XXX	xx.XXX	xx.XXX	0.XXX				
Treatment	Overall	x	xx.XXX	xx.XXX	xx.XXX	0.XXX				

									95% CI 	
Parameter		DF 	Estimate	Standard Error	Wald Chi-Square	Pr > Chi-Square	Cohen's h	OR 	Upper CI	Lower CI
Treatment 	ASP8062	x	xx.xxx	xx.xxx	xx.xxx	0.xxx	0.xxx	xx.xxx	xx.xxx	xx.xxx
Site	Overall	x	xx.xxx	xx.xxx	xx.xxx	0.xxx				
Site 	1	x	xx.xxx	xx.xxx	xx.xxx	0.xxx		xx.xxx	xx.xxx	xx.xxx
Site	2	x	xx.xxx	xx.xxx	xx.xxx	0.xxx		xx.xxx	xx.xxx	xx.xxx
Cov		x	xx.xxx	xx.xxx	xx.xxx	0.xxx		xx.xxx	xx.xxx	xx.xxx

 Nicotine use includes either cigarettes or other nicotine products;  DF is degrees of freedom;  OR is odds ratio;  CI is confidence interval;  Comparison to placebo for each active treatment;  Site 3 is reference for the OR

*Programming note: COV is baseline equivalent of dependent variable and any other covariate(s) which have not been specified at the time of writing of SAP*

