**Table 90: Percentage of Subjects Abstinent from Smoking Weeks 3-6 – Among Baseline Smokers**

Same analysis as Table 88

**Table 91: Percentage of Subjects Abstinent from Smoking Weeks 3-6 – Full Model Logistic Regression (Among Baseline Smokers)**

Same analysis as Table 89

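### Wald tests from ordinary logistic regression (SAP Tables 67, 69, 89 and 91) fail if one arm has no events, and the plan names no alternative

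*SAP*

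**What the plan says.** The protocol synopsis says that the analysis of the dichotomous secondary endpoints "during the last 4 weeks of treatment period will be conducted via logistic regression". The endpoints include no heavy drinking days, alcohol abstinence and no nicotine use.

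The SAP shells carry this out:

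- **Table 67**, "Percentage of Subjects with No Heavy Drinking Days Weeks 3-6 – Full Model Logistic Regression (mITT"), has columns for estimate, standard error, Wald chi-square, p-value, Cohen's h, odds ratio and 95% CI, with treatment, site and covariates in the model.
- **Table 69** (alcohol abstinence): "Presented in same manner as Table 67".
- **Table 89** (nicotine abstinence), "Full Model Logistic Regression (Among Nicotine Users at Baseline"), has the same Wald columns.
- **Table 91**, "Percentage of Subjects Abstinent from Smoking Weeks 3-6 – Full Model Logistic Regression (Among Baseline Smokers"), repeats Table 89.

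No penalised, exact or likelihood-ratio method is named for these four tables, so ordinary maximum likelihood is inferred from that silence. In the SAP text, the sentence "The Wald statistic will be used to test for treatment differences" (9.4.3.1) belongs to the WHO risk-level endpoints. For the four tables here, the evidence is the shell columns.

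Two provisions deal with few events. The protocol synopsis and SAP 9.4.4 let the number of covariates depend on the number of events. SAP 9.4.3.3 says of nicotine: "There will be one logistic regression, if there are sufficient number of subjects abstaining from nicotine use".

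SAP 9.4.3.1 also opens its list of mixed-model endpoints with "Percentage of days abstinent per week, percentage of subjects abstinent, percentage of heavy drinking days per week". That puts a yes/no endpoint, the percentage of subjects abstinent, under the mixed model, against the protocol and Table 69.

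**The concern.** An arm with no events is separation on the treatment term. The log odds ratio has no finite maximum-likelihood estimate. Its standard error grows faster than the estimate, so the Wald statistic shrinks toward zero as the fit iterates, and the odds ratio, interval and p-value depend on where the software stops.

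Neither sparse-data provision cures this. Dropping covariates leaves the treatment term, which is where the empty cell lies. The nicotine condition has no threshold, can be met with all abstainers in one arm, and names no test for when it is not met.

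Events may be few. Subjects enter drinking on average at least 28 (men) or 21 (women) drinks per week, and the alcohol endpoints require four weeks without a heavy drinking day or without any drinking. Tables 66 and 68 show counts without a test, and Figures 1 and 2 mark significance with an asterisk. A clear difference against an empty arm would therefore go unmarked, or the test would be chosen after unblinding.

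**Working it through.** **Inputs.** From the documents: 30 per arm (SAP section 7), which is a ceiling because the mITT set drops subjects without the primary VAS score; two-sided 0.05 (SAP 9.1); three sites. The 87% power in SAP section 7 concerns the primary ANCOVA only. There is no planned rate, event count or power for these endpoints to reproduce, so **every event rate below is an assumption**, as is the number of nicotine users.

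**1. How often an arm is empty.** P(no events among n) = (1 − p)^n. At equal rates, P(at least one empty arm) = 1 − [1 − (1 − p)^n]².

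| True rate | n per arm | One given arm empty | At least one arm empty |
|---|---|---|---|
| 3% | 30 | 40% | 64% |
| 5% | 30 | 21% | 38% |
| 10% | 30 | 4% | 8% |
| 20% | 30 | 0.1% | 0.2% |
| 10% | 10 (assumed nicotine users) | 35% | 58% |
| 20% | 10 (assumed nicotine users) | 11% | 20% |

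**2. What the planned test returns at 6/30 versus 0/30.** Newton iterations of the unadjusted model:

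| Iterations | Log OR | SE | Wald p |
|---|---|---|---|
| 8 | 7.8 | 18 | 0.67 |
| 15 | 14.8 | 602 | 0.98 |
| 25 | 24.8 | 89,398 | 1.00 |

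Fisher's exact p is 0.024. Even 10/30 versus 0/30 (Fisher p = 0.0008) gives a Wald p of at least 0.64.

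**3. The alternative on the same data.** With treatment only, the Firth estimate equals adding 0.5 to each cell: OR = (6.5/24.5)/(0.5/30.5) = 16.2. The penalised likelihood-ratio p is 0.009 (0.011 with three sites in the model), and the profile-likelihood 95% CI is 1.77 to 2150. The interval is very wide, but it exists and excludes 1. At 5/10 versus 0/10: Wald p about 1, Fisher 0.033, Firth 0.011, OR 21.0 (1.83 to 2956).

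**4. Power.** Exact enumeration of all 31 × 31 outcomes, unadjusted, with Wald p set to 1 when an arm is empty:

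| Assumed rates | Wald | Fisher | Firth LR |
|---|---|---|---|
| 3% vs 20% | 17% | 34% | 54% |
| 5% vs 25% | 34% | 44% | 58% |
| 10% vs 30% | 40% | 37% | 49% |
| 20% vs 40% | 36% | 30% | 39% |
| 20% vs 50% | 68% | 60% | 69% |

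With 10 per arm at 20% versus 50%: Wald 16%, Fisher 13%, Firth 25%.

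**5. Type I error, Wald / Firth.** 0.0% / 2.7% at a common rate of 5%; 0.8% / 4.1% at 10%; 3.4% / 4.6% at 20%; 4.1% / 4.9% at 30%. Firth's gain does not come from exceeding 5%.

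**6. With site in the model** (three equal sites, 4,000 simulated trials), Wald / Firth power is 18% / 55% at 3% vs 20%, 37% / 63% at 5% vs 25%, 43% / 50% at 10% vs 30%, 39% / 39% at 20% vs 40%, and 69% / 69% at 20% vs 50%.

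**The case against.** - **The trigger may not occur.** Subjects are treatment seeking, and both arms view the Take Control modules. Nothing in the documents establishes rates of 5% or less. At 20% or more in the lower arm the two methods nearly agree. This stands, and it limits the size of the point, but the plan gives no rates that rule sparse events out.
- **A one-line fallback might suffice.** Keeping the Wald test and switching to Fisher's exact test when an arm is empty fits the SAP, which already uses Fisher for disposition, exit-interview and dropout tables. By exact enumeration it gives 40% power at 3% vs 20%, 51% at 5% vs 25% and 44% at 10% vs 30%. That is better than Wald alone, but below Firth, and Fisher supplies no adjusted odds ratio or interval.
- **Firth declares sparse results more readily.** At 4/30 versus 0/30 its p is 0.047 (Fisher 0.11), and at 5/30 versus 0/30 it is 0.021 (Fisher 0.052). This is true, and the team should choose the method knowing it, since these endpoints carry no multiplicity adjustment. The type I error nevertheless stayed below 5% in every case run.
- **Nicotine is partly covered** by the condition in 9.4.3.3. That softens the point for Tables 89 and 91, so it is strongest for Tables 67 and 69.
- **The harm is limited.** The endpoints are secondary, the error is conservative, a diverging estimate is visible in the output, and counts and Cohen's h survive. All of this stands.

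**Conclusion.** The concern holds, as something that should be fixed. With an empty arm, the planned p-value, odds ratio and interval for these endpoints are unusable, and the plan names nothing to replace them. The loss is large if the lower-arm rate is about 5% or less, or if there are few nicotine users. It is modest at 10% and negligible at 20% or more with 30 per arm. These sizes rest on assumed rates and on reading the plan's silence as ordinary maximum likelihood. The primary conclusion is not affected and there is no inflation of false positives. The conflict over the model for alcohol abstinence is a separate defect that holds at any event rate.

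**What to change.** Before unblinding, amend SAP 9.4.3.1 and 9.4.3.3 and shells 67, 69, 89 and 91:

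1. Fit these endpoints by Firth penalised-likelihood logistic regression with the same site and covariate terms.
2. Test treatment by the penalised likelihood-ratio test and report profile-likelihood 95% CIs in place of the Wald statistic and interval. The pairing matters: Firth with Wald inference gives p = 0.062 and CI 0.87 to 302 at 6/30 versus 0/30.
3. Remove the percentage of subjects abstinent from the mixed-model list in 9.4.3.1. Name it, with no heavy drinking days, under logistic regression.

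Extending this to the WHO Tables 71 and 73 is optional, for consistency.

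The cost is text in two sections, column headings in four shells (six with the WHO tables) and a Firth option in the SAS logistic procedure. No new data are needed. Odds ratios shrink slightly: at 12/30 versus 6/30, (12.5/18.5)/(6.5/24.5) = 2.55 instead of (12/18)/(6/24) = 2.67.
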